#### Glibenclamide 5 mg

- Guidance for all patients → Take with breakfast or the main meal of the day at the same time each day. Should only be taken with food. Do not take on days that you are fasting, not able to eat, or if you will be eating significantly less food than you normally eat.
- Dosing
  - 2.5 mg (starting dose) → Take ½ tablet (2.5 mg) once daily with breakfast or the first main meal
    of the day
  - $\circ~~5~\text{mg} \rightarrow$  take one tablet once daily with breakfast or the first main meal of the day
  - $\circ~$  10 mg  $\rightarrow$  take two tablets daily with breakfast or the first main meal of the day

#### Hypoglycemia teaching for patients taking glibenclamide69

- Glibenclamide can cause low blood sugar, which sometimes can be dangerous
- Low blood sugar can cause symptoms such as shaking/tremors, feeling confused, feeling uncoordinated, sweating a lot more than normal, feeling very anxious for no reason, or heart beating fast or irregular. These usually come on suddenly and happen when you haven't eaten for a while, when doing hard physical work or exercising, or while drinking alcohol.
  - How to avoid low blood sugar
  - Eat regular meals
    - Take glibenclamide with the first main meal of the day and try to take at the same time each day.
       Do not taking if you will be fasting, not able to eat, or eating a lot less than you normally do.
    - Eat a snack with carbohydrates before doing hard physical work or exercising
    - Avoid drinking alcohol
  - If you think your blood sugar is low, you should eat or drink one of the following items:
    - 1 tablespoon of sugar
    - 6 hard candies
    - 2 tablespoons of raisins
    - 1 tablespoon of honey

    - $\circ \quad 1 \text{ cup of skim milk} \\$
    - /2 cup of regular soda (not diet soda)
- You should have at least one of these items with you when you leave the house so you can treat symptoms if you need to
- Sometimes, a person with very low blood sugar becomes so confused or sleepy that they can't eat or drink anything. Teach your family that if this happens to you, they should sprinkle sugar under your tongue and call for an ambulance right away.
- Let your health promoter know if you are having symptoms of low blood sugar and if these get better when you eat or drink something with sugar. If someone had to help you because you were very sleepy or confused, you should get help right away. You should not take your glibenclamide again until you see your health promoter.

## **Appendix 10 - Monthly Medication Dosing Recommendations**

Version #: 1.0

[name]

#### FBG <80 (<90) or PPBG<130(150)

- 1. Metformin without problems, adherent  $\rightarrow$  continue current doses
- 2. Metformin without problems, nonadherent
  - a. Metformin 850 mg  $\rightarrow$  metformin 850 mg
  - b. Metformin 1700-2550 mg → metformin 1700 mg
- 3. Metformin with problems, adherent
  - a. Metformin 850 mg, willing to continue  $\rightarrow$  Metformin 850 mg
  - b. Metformin 850 mg, not willing to continue  $\rightarrow$  stop medications, check A1c when next indicated
  - c. Metformin 1700 mg  $\rightarrow$  metformin 850 mg
  - d. Metformin 2550 mg  $\rightarrow$  metformin 1700 mg
- 4. Metformin with problems, nonadherent  $\rightarrow$  same as #3
- Glibenclamide without problems, no previous problems with metformin, took yesterday → metformin 1700 mg
- Glibenclamide without problems, no previous problems with metformin, did not take yesterday → metformin 1700 mg
- 7. Glibenclamide without problems, previous problems with metformin, took yesterday
  - a. Agrees to take metformin
    - i. Glibenclamide 2.5-5 mg  $\rightarrow$  metformin 850 mg
    - ii. Glibenclamide 10 mg → metformin 850 mg + glibenclamide 2.5 mg
  - b. Refuses to take metformin
    - i. Glibenclamide 2.5 mg  $\rightarrow$  stop medications, recheck A1c in 3 months
    - ii. Glibenclamide 5 mg  $\rightarrow$  glibenclamide 2.5 mg
    - iii. Glibenclamide 10 mg  $\rightarrow$  glibenclamide 5 mg
- 8. Glibenclamide without problems, previous problems with metformin, did not take yesterday
  - a. Agrees to take metformin  $\rightarrow$  metformin 850 mg
  - b. Refuses to take metformin  $\rightarrow$  stop medications, recheck A1c in 3 months
- Glibenclamide with hypoglycemia or hypoglycemia symptoms, no previous problems with metformin, took vesterday → metformin 1700 mg
- 10. Glibenclamide with hypoglycemia or hypoglycemia symptoms, no previous problems with metformin, did not take yesterday → metformin 1700 mg
- Glibenclamide with hypoglycemia or hypoglycemia symptoms, previous problems with metformin, took yesterday → same as #8
- Glibenclamide with hypoglycemia or hypoglycemia symptoms, previous problems with metformin did not take yesterday → same as #8
- 13. Metformin and glibenclamide without problems, adherent, took glibenclamide yesterday
  - a. Metformin 850 mg + glibenclamide any dose  $\rightarrow$  metformin 1700 mg
  - b. Metformin 1700-2550 mg + glibenclamide 2.5 mg  $\rightarrow$  metformin 1700 mg
  - c. Metformin 1700-2550 mg + glibenclamide 5 mg  $\rightarrow$  metformin 1700 mg + glibenclamide 2.5 mg
  - d. Metformin 1700-2550 mg + glibenclamide 10 mg  $\rightarrow$  metformin 1700 mg + glibenclamide 5 mg
- 14. Metformin and glibenclamide without problems, nonadherent, took glibenclamide yesterday  $\rightarrow$  same as #13
- 15. Metformin and glibenclamide without problems, adherent, did not take glibenclamide yesterday  $\rightarrow$  metformin 1700 mg

<sup>18 Numbers in parentheses refer to the relevant measurements for patients who have relaxed glycemic goals (A1c ≤8, FBG 90-150, PPBG <200)

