# 6.5 Starting Dose and Dose Escalation Schedule

Metformin will be started at 850 mg once daily and increased to the target dose of 1700 mg after 2 weeks. If not meeting treatment goals after ≥1 month, metformin can be increased to 2550 mg. Patients who are unable to tolerate the 1700 mg dose will take the 850 mg dose.

Version #: 1.0

[name]

Glibenclamide will be used for patients who are unable to tolerate metformin, in addition to metformin if A1c  $\geq$ 9, or if glycemic goals not met despite maximal dose of metformin. Dosing will start at 2.5 mg once per day. If glycemic goals are not met after  $\geq$ 1 month, dose will be escalated to 5 mg once per day and then 10 mg once per day as needed.

Aspirin will be dosed at 81 mg once per day for secondary prevention in eligible patients with history of MI or stroke or patients who have new chest pain and are awaiting medical workup for possible CAD. Patients with high risk chest pain and possible ACS will be treated with aspirin 324 mg (four 81 mg tablets) once while awaiting emergency transport to SLMH.

Please consult Appendix 8, Appendix 10, and Appendix 11 for further information on medication titration protocols

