#### [name]

- If NO, "How many milligrams of Glibenclamide do you take in total per day " (numeric entry box)
- "Are you taking any other medication for diabetes prescribed by a doctor " (Y/N)
- If NO, application skips to next question
  - If YES, application prompts promoter to enter medication name (free text), milligram strength of pills (numeric entry), and number of pills per day (½, 1, 2, 3, or 4)
- If patient not currently taking any medication, application prompts promoter to ask, "Have you previously taken medication for diabetes " (Y/N)
  - If YES, questions regarding medication side effects appear (These also appear if patient is taking any of the aforementioned medications)
  - If NO, application skips to the next section
  - "Are you currently taking medication for high blood pressure " (Y/N)
  - If YES
    - Application prompts promoter to collect information about name of medication (free text) and dosage (numeric entry)
    - Renal function testing will be recommended for this patient
    - Application skips to the next section
    - If NO, application skips to the next section

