#### Assessing for Medication Side Effects

- "Have you had any side effects from your medications " (Y/N)
  - If NO, application skips to the next section
  - $\circ~$  If YES, application prompts promoter to ask the patient: "What problems have you had with your medication "\*
  - Application asks promoter: "Has the patient complained of nausea, vomiting, or persistent diarrhea after taking Metformin " (Y/N)
    - If YES, application prompts promoter to ask patient: "Have you skipped a dose of metformin, or thought about stopping metformin due to these symptoms "
      - If YES, patient is considered to be having significant metformin side effects
      - If NO, patient is not considered to be having significant metformin side effects
    - If NO, application prompts promoter to enter other symptoms in a free text box for review by the physician
  - For patients taking aspirin (for monthly visit only): "In the past month, have you had blood in your stool or stool that is very black and tarry."
    - If YES, patient is advised to stop aspirin and is referred to medical director for further assessment
    - If NO, aspirin is continued

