#### 9≤ A1c ≤14

- 1. Not taking medications  $\rightarrow$  metformin 1700 mg + glibenclamide 2.5 mg
- 2. Not taking medications, problems with metformin
  - a. Agrees to take metformin → metformin 850 mg + glibenclamide 2.5 mg
  - b. Refuses to take metformin  $\rightarrow$  glibenclamide 2.5 mg
- 3. Not taking medications, hypoglycemia or hypoglycemia symptoms  $\rightarrow$  metformin 1700 mg
- 4. Not taking medications, hypoglycemia or hypoglycemia symptoms, problems with metformin
  - a. Agrees to take metformin, prescribed glibenclamide >2.5 mg  $\rightarrow$  metformin 850 mg + glibenclamide 2.5 mg
  - b. Agrees to take metformin, prescribed glibenclamide 2.5 mg  $\rightarrow$  metformin 850 mg
  - c. Refuses to take metformin, prescribed glibenclamide >2.5 mg  $\rightarrow$  glibenclamide 2.5 mg
  - d. Refuses to take metformin, prescribed glibenclamide 2.5 mg  $\rightarrow$  MD consult
- 5. Taking metformin without problems
  - a. Metformin 500-2000 mg  $\rightarrow$  metformin 1700 mg + glibenclamide 2.5 mg
  - b. Metformin 2550 mg  $\rightarrow$  metformin 2550 mg + glibenclamide 2.5 mg
- 6. Taking metformin with problems
  - a. Metformin 500-850 mg, agrees to take metformin  $\rightarrow$  metformin 850 mg + glibenclamide 2.5 mg
  - b. Metformin 500-850 mg, refuses to take metformin  $\rightarrow$  glibenclamide 2.5 mg
  - c. Metformin 1000-1700 mg  $\rightarrow$  metformin 850 mg + glibenclamide 2.5 mg
  - d. Metformin 2000-2550 mg  $\rightarrow$  metformin 1700 mg + glibenclamide 2.5 mg
- 7. Taking glibenclamide without problems
  - a. Glibenclamide 2.5-10 mg → metformin 1700 mg +glibenclamide current dose
  - b. Glibenclamide 15-20 mg  $\rightarrow$  metformin 1700 mg + glibenclamide 10 mg
- 8. Taking glibenclamide without problems, previous problems with metformin
  - a. Agrees to take metformin
    - i. Glibenclamide 2.5-10 mg → metformin 850 mg + glibenclamide current dose
    - ii. Glibenclamide 15-20 mg  $\rightarrow$  metformin 850 mg + glibenclamide 10 mg
  - b. Refuses to take metformin
    - i. Glibenclamide 2.5 mg  $\rightarrow$  glibenclamide 5 mg
    - ii. Glibenclamide 5 mg  $\rightarrow$  glibenclamide 10 mg
    - iii. Glibenclamide 10-20 mg  $\rightarrow$  glibenclamide 10 mg
- 9. Taking glibenclamide with hypoglycemia or hypoglycemia symptoms
  - a. Glibenclamide 2.5 mg  $\rightarrow$  metformin 1700 mg
    - b. Glibenclamide 5 mg  $\rightarrow$  metformin 1700 mg + glibenclamide 2.5 mg

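### The glibenclamide-only dosing rows depend on an earlier metformin problem that Appendix 3 records only if the patient volunteers it, so a metformin-intolerant patient can be routed back to metformin 1700 mg without being asked.

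*Combined protocol and SAP*

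**What the plan says.** **Dosing tables.** In the lowest glucose band of Appendix 10, row 5 is headed "Glibenclamide without problems, no previous problems with metformin, took yesterday" and gives metformin 1700 mg. Rows 7, 8, 11 and 12 of that band cover patients with an earlier metformin problem and first split on whether the patient will take metformin. Appendix 8 makes the same distinction at enrollment; for A1c 9 to 14, row 8 is headed "Taking glibenclamide without problems, previous problems with metformin". Appendix 11 repeats it for the quarterly visits.

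**Data capture (Appendix 3).** The question on past diabetes medication is conditional: "If patient not currently taking any medication, application prompts promoter to ask" it. The side-effect items have wider reach: "These also appear if patient is taking any of the aforementioned medications". They open with "Have you had any side effects from your medications", and the instruction is "If NO, application skips to the next section". Only after a YES does the health worker reach "Has the patient complained of nausea, vomiting, or persistent diarrhea after taking Metformin" and then the item that establishes significant metformin side effects. Footnote 8 explains that the opening question is deliberately unspecific.

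**Follow-up (section 7.4.2, Monthly Visits).** Demographics and medical history are carried over from enrollment. Nothing is said about carrying over a metformin problem, and the Past Medical History list in Appendix 1 has no such item.

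**Role of glibenclamide (section 6.5).** "Glibenclamide will be used for patients who are unable to tolerate metformin".

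**The concern.** The variable that decides the regimen is not defined, is not asked about directly in the patients for whom it matters, and has no stated memory. Many of those patients are known to the program: its own tables move a patient from metformin to glibenclamide alone when the patient has metformin problems and declines the lowest metformin dose. A month later the same patient may be well on glibenclamide and report no side effects.

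At stake is first a safety and adherence matter: metformin being dispensed again to someone who stopped it for intolerance, without the step that asks whether they will take it. It also touches secondary endpoints in section 4.1.2 (metformin adverse effects, referrals for intolerance, adherence). Section 4.1.3 counts incorrect application recommendations as a primary safety endpoint, but a recommendation that follows the table correctly from an incomplete history might not be counted as one.

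**Working it through.** No power, alpha or event figure bears on this. The check is a trace of the skip logic and a count of rows.

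**Step 1: trace of Appendix 3 for a patient on glibenclamide only.** Metformin now: NO. Glibenclamide now: YES. The past-medication question is not shown, because the patient takes a drug. The side-effect block is shown.
- (a) Opening answer NO: the block is skipped and nothing about metformin is recorded.
- (b) Opening answer YES, and the patient volunteers stomach or bowel trouble from metformin: the metformin items are reached and a problem can be recorded.
- (c) Opening answer YES, but about something else: the answer goes to free text for physician review.

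The history is obtainable on path (b) and missed on (a) and (c). Section 10.3 describes the same opening question as the way to assess effects of medications the patient is taking in the program. On that reading, NO is a correct answer from someone who has left metformin and is well on glibenclamide.

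**Step 2: how patients come to be on glibenclamide alone.** Rows that take a patient from metformin to glibenclamide alone sit under a metformin-problem heading, for example Appendix 8, A1c 9 to 14, row 6b; Appendix 10, FBG 130(150) to 180(200), row 3b; Appendix 11, A1c 6 to goal, row 3b. The program has therefore recorded the problem once, but no text says that the record is read at the next visit.

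**Step 3: what the no-history rows give.** In Appendix 10 these are rows 5, 6, 9 and 10.

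| Appendix 10 band (FBG) | Rows giving metformin 1700 mg, alone or with glibenclamide | Rows continuing glibenclamide unchanged |
|---|---|---|
| below 80(90) | 4 of 4 | 0 |
| 80(90) to 130(150) | 3 of 4 | 1 (row 5) |
| 130(150) to 180(200) | 2 of 4 | 2 (rows 5, 6) |
| 180(200) to 400 | 4 of 4 | 0 |

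Total: 4 + 3 + 2 + 4 = 13 of 16. In the other three rows the matching row for patients with a metformin history (row 7, and rows 7 and 8, respectively) also continues the current dose, so a wrong classification changes nothing there. In the 13 it changes the output.

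Appendix 11, same row numbers over its four full A1c bands: 2 + 4 + 4 + 4 = 14 of 16 give metformin 1700 mg; the other two stop medication. In Appendix 8, the rows for glibenclamide-only patients without a metformin history number 1 + 1 + 2 + 2 + 2 = 8 over the five A1c bands, and all 8 give metformin 1700 mg, alone or with glibenclamide.

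**The case against.** Much of the case against a stronger claim is sound.

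- **A reader might infer that Appendix 3 cannot collect the history at all.** It can. The side-effect block is open to glibenclamide users, and its metformin item is not limited to current metformin users. The opening question also has no time limit, unlike the adherence and hypoglycemia questions, so some patients may mention an old metformin problem.
- **A reader might infer that a missing answer defaults to the 1700 mg row.** No default is stated. Silence on carry-forward also does not prove that the application stores nothing.
- **A reader might infer that rows 5, 6, 9 and 10 are reachable only through a missed history.** Not so. A physician may change a regimen, or a patient on both drugs may stop metformin for another reason.
- **A reader might see a contradiction of section 6.5.** That section says when glibenclamide is used, and the rows for patients with a metformin history carry it out. The fault is in the input to those rows.
- **The harms are easily overstated.** In the lowest band, correctly classified patients can also lose glibenclamide or stop all medication. Section 6.5 and Appendix 9 start metformin at 850 mg for two weeks, so 1700 mg is not immediate.
- **Safeguards exist.** Section 2.7.2 and Appendix 7 refer patients who cannot tolerate the drugs, telephone advice is available, and the physician reviews each visit within 1 week.

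The safeguards do not close the gap. Review follows dispensing and uses the same visit data. Referral requires the intolerance to be recognized. Testing each scenario in the application cannot supply an input that was never collected.

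**Conclusion.** The point holds as a faulty input rule. Followed as written, Appendix 3 lets a patient who left metformin for intolerance, and who answers NO about current drugs, be treated as having no metformin history. That patient can then reach a row giving metformin 1700 mg without the willingness step: 13 of 16 such rows in Appendix 10, and all 4 in its lowest band.

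This rests on two assumptions: that some patients read the open question as concerning what they take now, and that no unstated stored field is read at later visits. The documents neither confirm nor exclude either.

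The number of patients cannot be derived. A reader might take the 5% in section 2.7.1 and write 5% × 100 = 5 patients at every visit. That figure is the share of metformin users who stop it completely. It is not the share of this sample on glibenclamide alone with an unreported history, and a patient given metformin leaves these rows at the next visit.

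**What to change.** In Appendix 3, ask every patient who takes glibenclamide but not metformin whether they took metformin before and, if so, why they stopped. Keeping the second part open-ended respects the reasoning in footnote 8, since no symptom is suggested. Define a metformin-problem field, store it at enrollment and whenever a row under a metformin-problem heading is used, and state that the glibenclamide-only rows of Appendices 8, 10 and 11 read it. If the application already holds such a field, saying so in section 7.4.2 settles the carry-forward part.

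How long the field should count, and what follows from it clinically, is for the investigators. They need to reconcile Appendix 3 with the dosing tables; no dose or clinical rule is proposed here.

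The cost is one question, one stored field and re-testing of the application.
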